## 10.1 Analysis sets

## 10.1.1 Full Analysis Set

The Full Analysis Set (FAS) includes all patients who received at least one dose of BGJ398. The FAS will be used for all listings of raw data. Unless otherwise specified, the FAS will be the default analysis set used for all analyses.

## 10.1.2 Interim Efficacy Analysis Set 1 for Cohort 1

The Interim Efficacy Analysis Set 1 for Cohort 1 includes all patients with planned extensive PK sample collection (regardless of whether extensive PK samples were actually collected) and all patients enrolled prior to amendment 2. Unless otherwise specified, the Interim Efficacy Analysis Set 1 will be used as the primary efficacy analysis set for the first formal interim analysis for Cohort 1 after amendment 3. Patients

will be classified according to their baseline genetic status (FGFR2 gene fusions or translocations only vs other FGFR genetic alterations).

## 10.1.3 Interim Analysis Set 2 for Cohort 1

The Interim Analysis Set 2 for Cohort 1 includes patients in Cohort 1 with FGFR2 gene fusions or translocations who have received at least one dose of BGJ398. Interim Analysis Set 2 for Cohort 1 will be used as the primary analysis set for the second formal interim analysis for Cohort 1 after amendment 3.

## 10.1.4 Sensitivity Analysis Set for Cohort 1

The Sensitivity Analysis Set for Cohort 1 includes patients with FGFR2 gene fusions or translocations who received BGJ398 at the time of the first formal interim analysis and patients who have disease progression according to central imaging review or ended treatment by the cutoff date for the second formal interim analysis for Cohort 1 after amendment 3. The cutoff date for the second formal interim analysis is planned so that all the patients with FGFR2 gene fusions or translocations who received BGJ398 at the time of the first formal interim analysis have 10 months follow-up after their initial exposure to BGJ398. The Sensitivity Analysis Set for Cohort 1 will be used for supportive sensitivity analyses for the second formal interim analysis for Cohort 1.

### 10.1.5 Interim Analysis Set for Cohort 3

The Interim Analysis Set for Cohort 3 will include the first 10 dosed patients who have the potential to complete second scheduled scan.

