The overall observation period will be divided into three mutually exclusive segments:

pre-treatment period: from day of subject's first informed consent to the day before first administration of study treatment

on-treatment period: from date of first administration of study treatment to 30 days after date of last actual administration of any study treatment (including start and stop date).

post-treatment period: starting at Day 31 after last administration of study treatment in the single arm.

If dates are incomplete in a way that clear assignment to pre-, on-, post-treatment period cannot be made, then the respective data will be assigned to the on-treatment period.

Safety summaries (tables, figures) include only data from the on-treatment period with the exception of baseline data which will also be summarized where appropriate (eg, change from baseline summaries). In addition, a separate summary for death including on-treatment and post treatment deaths will be provided. Summary tables for adverse events (AEs) will summarize only on-treatment events, with a start date during the on-treatment period (***treatment-emergent AEs***).

2.1.1.6 *Handling of Missing Values/Censoring*

Subjects who are of unknown clinical response or not assessed will be treated as nonresponders in the analyses of overall response rate (ORR).

Subjects who haven't experienced the specified event at the time of analysis will have time-to-event data (eg, progression-free survival, overall survival, etc.) censored at the time of last measurement prior to the data cut-off point used in the report.

2.2 *Analysis Sets*

2.2.1 *Full Analysis Set*

The Full Analysis Set (FAS) includes all subjects who received at least one dose of infigratinib. Unless otherwise specified, all the analyses will be done separately for each cohort.

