Unless otherwise specified, all the analyses will be conducted on FAS. All efficacy related analyses will be done separately for all subjects, subjects with baseline FGFR2 gene fusions or translocations and subjects with only other FGFR genomic alterations. In addition, for subjects with baseline FGFR2 gene fusions or translocations, the data will be summarized by treatment (formulation FMI I vs FMI III vs FMI IV). The analyses, including safety, disposition, demographic/baseline disease characteristics, study drug exposure and prior/concomitant/post therapy related analyses, will be done separately for all subjects, all subjects by FGFR status (FGFR2 gene fusion/translocation vs. only other FGFR genomic alterations) and all subjects by treatment.

Unless otherwise specified, the FAS will be used for all listings of raw data.

2.2.2 Interim Efficacy Analysis Set 1 for Cohort 1

The Interim Efficacy Analysis Set 1 for Cohort 1 includes all subjects with planned extensive PK sample collection in Cohort 1 (regardless of whether extensive PK samples were actually collected) and all patients enrolled prior to Amendment 2. Unless otherwise specified, the Interim Efficacy Analysis Set 1 will be used as the primary efficacy analysis set for the first formal interim analysis for Cohort 1 after Amendment 3. Patients will be classified according to their baseline genetic status (FGFR2 gene fusions or translocations vs only other FGFR genetic alterations).

2.2.3 Interim Analysis Set 2 for Cohort 1

The Interim Analysis Set 2 for Cohort 1 includes patients in Cohort 1 with FGFR2 gene fusions or translocations who have received at least one dose of infiratinib. Interim Analysis Set 2 for Cohort 1 will be used as the primary analysis set for the second formal interim analysis for Cohort 1 after Amendment 3.

2.2.4 Sensitivity Analysis Set for Cohort 1

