Compliance to the study treatment will be summarized in terms of the RDI or percentage of patients who took a predefined percentage of the number of prescribed. The predefined RDI categories are ≤ 0.5 , $>0.5 - \leq 0.75$, $>0.75 - \leq 0.9$, $>0.9 - \leq 1.0$ and >1.0 . The number and proportion of patients falling in each category will be presented. Details are provided in Section [2.5.1](#).

2.6 *Analysis of the primary objective*

2.6.1 *Variable*

For Cohort 1, the primary objective of the study is to assess anti-tumor activity of infigratinib using overall response rate assessed by central imaging review.

Best overall response (BOR) is the best overall response a subject ever achieves during the study prior to any subsequent anti-cancer therapy. Overall response rate (ORR) is defined as the proportion of patients with a best overall response of confirmed Complete Response (CR) or Partial Response (PR), as per RECIST version 1.1, among the corresponding analysis set.

ORR (central imaging assessment) is the primary efficacy endpoint, and its analysis consists of a Clopper-Pearson 95% CI accompanied by a characterization of time to response (TTR) and duration of response (DOR) to allow for a more complete characterization of the beneficial effect Infigratinib may have in the principal analysis population. The Brookmeyer-Crowley method will be used to construct the 95% CI for each of TTR and DOR.

2.6.2 *Statistical Hypothesis, Model, and Method of Analysis*

For Cohort 1, the primary analysis of the primary endpoint (ORR assessed by central imaging review) should occur when all subjects in Cohort 1 have the potential to be followed for at least 10 months after their initial exposure to study treatment. The formal interim analysis for Cohort 1 will be conducted when all patients in the interim efficacy analysis set have been followed for at least 10 months after their initial exposure to the study treatment. Any confirmed PR or CR until the data cut-off date and any subsequent anti-cancer therapy will be considered as a responder for ORR, irrespective of when it occurred.

2.7 *Analysis of Secondary Objective(s)*

This section describes analyses of secondary objectives for Cohort 1. The same endpoints will be analyzed for Cohorts 2 and 3 as exploratory, so the approaches described in this section also apply to Cohort 2 and 3.

2.7.1 *Secondary Efficacy Objectives*

Overall Response Rate Per Investigator

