2.9 Interim Analysis

Safety and efficacy data will be continuously monitored by QED Therapeutics in conjunction with the investigators for decision-making purposes.

For Cohort 1, one analysis was performed before Amendment 2 based on the 61 patients enrolled in the study (30 Jun 2016). Protocol amendment 2 restricted enrollment to patients with FGFR2 fusions or translocations, and the formulation was changed from FMI I to FMI III.

After 20 subjects had been treated with FMI III (for at least one cycle) based on Amendment 2, a comprehensive review of all relevant data such as PK, safety, dose interruptions/reductions, and available efficacy was performed. PK, safety, and tolerability data from the first 20 subjects treated with FMI III up to the end of cycle 1 of treatment were assessed and compared with the historical data from subjects treated with FMI I. Upon review of the data, it was decided to continue dosing all subsequent patients treated with FMI III at 125 mg on a 3 weeks on, 1 week off schedule.

In addition, two formal interim analyses for Cohort 1 are planned after Amendment 3:

- The first formal interim analysis for Cohort 1 was conducted when all patients in the Interim Efficacy Analysis Set 1 have been followed for at least 10 months after their initial exposure to the study treatment. This interim analysis will be done using only patients in Cohort 1. Efficacy analysis for this interim analysis will be based on the Interim Efficacy Analysis Set 1 and some key efficacy analyses may be repeated in the FAS. All the other analyses will be conducted on FAS unless otherwise specified.
- The second will be conducted when all the patients who received infiratinib at the time of the first formal interim analysis have at least 10 months follow-up after their initial exposure to infiratinib.

Additionally, for Cohorts 2 and 3, review of data will be performed after a total of 15 patients in either Cohort 2 or 3 have been treated with FMI IV for at least one cycle. A formal interim analysis will be conducted for Cohort 3 when the first dosed 10 patients in Cohort 3 have the potential to complete the second scheduled scan. This interim analysis will only include data from Cohort 3. This is to determine if an additional 10 patients will be added to Cohort 3.

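### The second Cohort 1 interim should add an ORR on fusion patients chosen by first-dose date, because its primary set has no minimum follow-up and counts patients too recently dosed to have a confirmed response

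*SAP*

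**What the plan says.** **Membership.** SAP 2.2.3 says that Interim Analysis Set 2 "includes patients in Cohort 1 with FGFR2 gene fusions or translocations who have received at least one dose of infiratinib", and that it "will be used as the primary analysis set for the second formal interim analysis for Cohort 1 after Amendment 3". Protocol 10.1.3 has the same rule: the set "includes patients in Cohort 1 with FGFR2 gene fusions or translocations who have received at least one dose of BGJ398". Neither text asks for a minimum time since first dose or for a post-baseline scan.

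**Timing.** Under SAP 2.9 the second interim falls when all patients "who received infiratinib at the time of the first formal interim analysis have at least 10 months follow-up". Patients first dosed after the first interim have no such guarantee.

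**Scoring.** SAP 2.6.1 defines ORR as the proportion with "a best overall response of confirmed Complete Response (CR) or Partial Response (PR), as per RECIST version 1.1, among the corresponding analysis set". SAP 2.1.1.6 counts patients with unknown or missing response as non-responders. Protocol 14.3.12 treats an unconfirmed PR as stable disease.

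**The other Cohort 1 analyses.** The first interim's efficacy set had at least 10 months of follow-up for all its patients (protocol 10.7, SAP 2.9). The primary analysis "should occur when all subjects in Cohort 1 have the potential to be followed for at least 10 months after their initial exposure" (SAP 2.6.2).

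**Sensitivity Analysis Set.** SAP 2.2.4 and protocol 10.1.4 take the fusion patients treated at the time of the first interim, and add patients who by the second cut-off have progressed on central review or stopped treatment. SAP 2.2.4 repeats some key efficacy analyses on this set.

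**The concern.** A patient dosed shortly before the second cut-off is in the ORR denominator but cannot yet be in the numerator. The resulting error is zero or downward, never upward. Patients past week 12 but short of 10 months may also be under-counted, if they would first respond at a later scan.

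What is at stake is comparability. The headline efficacy sets of the first interim and of the primary analysis carry a 10-month rule for every patient; Set 2 does not. A lower ORR at the second interim could then reflect immature follow-up rather than a different response rate. No planned set for this interim selects patients purely by date of first dose.

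**Working it through.** **1. The plan's own precision figures.** SAP 3.1 gives a half-width of the exact 95% CI below 10% for 106 fusion patients and not above 12% for 72. Taking the largest Clopper-Pearson half-width over all possible counts gives 9.87 points for n = 106 (at 53 responders) and 12.02 points for n = 72 (at 36 responders). The first figure reproduces; the second does after rounding. Both describe width only and say nothing about immature patients.

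**2. Earliest confirmed response.** The first scheduled scan is Cycle 3 Day 1, which is day 57 with 28-day cycles. Confirmation needs at least 4 more weeks (protocol 7.2.1). That gives 8 + 4 = 12 weeks after first dose. It is 11 weeks if the first scan uses the −7-day window of protocol 7.2.1; protocol 7.1 allows only +7 days for that scan.

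**3. Does the plan expect under-followed patients?** Yes. The 14 non-fusion patients in Cohort 1 all enrolled before amendment 2, so only later fusion patients could be short of 10 months. If there were none, the second interim's trigger would coincide with that of the separate primary analysis, and the part of the Sensitivity Analysis Set for later patients would be empty. This does not show how many would have under 12 weeks.

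**4. Expected loss.** Let N be the set size, k the number too recently dosed for a confirmed response, and p the mature ORR. Expected ORR is p(N − k)/N, so the loss is p × k/N. N = 106 is the planned number. The documents give neither k nor an expected ORR, so p is assumed. The 15.5% row uses the only ORR in the documents (amendment 2 rationale), which is investigator-assessed, from 58 evaluable patients and not fusion-only; it serves only as a low end.

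| Loss in points | k = 0 | k = 5 | k = 10 | k = 20 | k = 34 |
|---|---|---|---|---|---|
| p = 15.5% | 0 | 0.7 | 1.5 | 2.9 | 5.0 |
| p = 25% | 0 | 1.2 | 2.4 | 4.7 | 8.0 |
| p = 40% | 0 | 1.9 | 3.8 | 7.5 | 12.8 |

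At p = 25% the binomial standard error for n = 106 is √(0.25 × 0.75/106) = 4.2 points.

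**5. How large could k be?** The first interim's efficacy set holds 72 of the 106 fusion patients, so k cannot exceed 106 − 72 = 34. That is only a ceiling: any of the 34 dosed by the first interim also has 10 months at the second. Two illustrations, assuming even accrual right up to cut-off and about 10 months (43.5 weeks) between the interims:
- The 34 spread over the 20 months (87 weeks) before the second cut-off: k ≈ 34 × 12/87 = 4.7, about 5.
- All 34 dosed between the two interims: k ≈ 34 × 12/43.5 = 9.4, a loss of 0.25 × 9.4/106 = 2.2 points at p = 25%.

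If accrual ended 12 weeks or more before cut-off, k = 0.

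**6. Effect on the interval.** With p = 25% and k = 10, expect 0.25 × 96 = 24 responders. Over the whole set, 24/106 = 22.6% (exact 95% CI 15.1 to 31.8). Over the 96 patients who could have a confirmed response, 24/96 = 25.0% (16.7 to 34.9).

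**7. Does the Sensitivity Analysis Set correct it?** No. Suppose p = 25% and 20 late patients, of whom 6 progressed or stopped without a response. The set then has 86 + 6 = 92 patients and 0.25 × 86 = 21.5 expected responders: 21.5/92 = 23.4%, not 25%. It adds early failures and leaves out late patients still on treatment who may yet respond.

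**The case against.** The strongest objection concerns size and consequence. The ceiling of k = 34 invites the reading that the interim ORR could be about 8 points too low at an ORR of 25%. The documents do not support that. It would need every fusion patient outside the first interim's efficacy set to have started within the last 12 weeks, and nothing in the text suggests such bunching. Even accrual gives about 1 to 2 points, well inside one standard error. This stands.

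Nor is any success boundary, futility rule or hypothesis attached to this interim; it is an estimate with an exact CI. A reader might infer that the trial's efficacy conclusion is compromised. It is not: the error is conservative, and the primary analysis waits for potential 10-month follow-up in everyone. This also stands.

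Third, all-dosed is the plan's default population, and Set 2 is also the safety set for this interim (SAP 2.7.2, 2.7.3). Replacing it as the headline set would drop patients with several scans, some perhaps confirmed responders. That is a fair argument against replacing Set 2, but not against adding a date-based estimate beside it.

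Fourth, the plan already has a sensitivity set, and the first interim repeated key efficacy analyses on the Full Analysis Set, which has no follow-up minimum either. Both are true. The sensitivity set nevertheless selects on outcome, and at the first interim the all-dosed result stood beside a set with full follow-up, which the second interim lacks.

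**Conclusion.** The point holds as a limited one. Set 2 can only understate the mature ORR, and the Sensitivity Analysis Set does not repair this, because later-dosed patients enter it through progression or stopping treatment.

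The size cannot be computed from the documents. At an assumed ORR of 25% with 106 patients, the loss is about 1.2 points for k = 5 and 2.2 to 2.4 points for k between 9 and 10, and zero if k = 0. These figures cover only the 12-week effect; late responses among patients between 12 weeks and 10 months could add to them by an amount that the documents do not allow to be estimated.

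The documents do not support calling the all-dosed set an error that must be replaced. The case is for one additional, better-matched estimate: a cheap improvement to a descriptive interim.

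**What to change.** Keep Set 2 for safety and for the all-dosed ORR. In SAP 2.2.4 and 2.9, add an ORR with exact 95% CI on fusion patients first dosed at least 10 months before the second interim cut-off, chosen by first-dose date only and whatever their outcome, so that early dropouts and early failures who meet the date stay in. Name it as the figure to compare with the first interim and the primary analysis. Report how many Set 2 patients have under 12 weeks and under 10 months of potential follow-up.

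The new set can stand alongside the Sensitivity Analysis Set or take its place. Alongside is the lighter route: a SAP edit, with an entry in SAP section 4, which now lists no changes from the protocol. Replacing that set would also touch protocol 10.1.4 and so need an amendment.

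The statistical cost is a smaller n, between 72 and 106. At an observed ORR of about 25%, the exact CI half-width is about 8.6 points with 26/106 (16.7 to 33.8), 9.1 with 24/96 (16.7 to 34.9) and 10.6 with 18/72 (15.5 to 36.6).

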2 STATISTICAL METHODS

2.1 Data Analysis General Information

Study data will be analyzed by QED Therapeutics and/or designated CRO(s) using the most updated SAS® version in the statistical computing environment. PK parameters will be calculated using non-compartmental methods available in Phoenix WinNonlin version 7.0 or higher.

Two formal interim analyses for Cohort 1 are planned after Amendment 3 as described in Section 2.9. The first formal interim analysis will include all patients in Cohort 1 who receive study treatment before the interim analysis cutoff date. The efficacy analysis for the first formal interim analysis for Cohort 1 will be focused on the population as described in Section 2.2.2 below. The second formal interim analysis will be conducted on all the subjects with FGFR2 fusions or translocations in Cohort 1. The primary analysis for Cohort 1 will be conducted when all patients in Cohort 1 have the potential to be followed for at least 10 months after their initial exposure to study treatment. For the interim and primary analyses for Cohort 1, patients will be grouped by fusion status (if subjects without FGFR2 fusions or translocations are included) and formulation. Here, the formulation refers to the first formulation a subject received if a subject switched formulation during the study as described in Section 1.1.

For Cohorts 2 and 3, review of data will be performed after a total of 15 patients in either Cohort 2 or 3 have been treated with FMI IV for at least one cycle. Primary analysis will be conducted when all patients in the cohorts have the potential to be followed for at least 10 months after their initial exposure to study treatment. Additionally, for Cohort 3, one interim analysis will be conducted after the first 10 dosed patients in this cohort have the potential to complete their second scheduled scans (approximately 16 weeks from their first dose) to determine if the cohort will be expanded.

The additional data for patients continuing to receive study treatment or remain in study past the data cutoff date of the primary analysis, as allowed by the protocol, will be reported in a final CSR that will be prepared at the end of the study. In the final CSR, analyses will be done for each cohort, for patients enrolled in Cohort 1 who do not have FGFR2 fusions or translocations, data may be combined and summarized with Cohort 2.

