The Sensitivity Analysis Set for Cohort 1 includes patients with FGFR2 gene fusions or translocations who received infiratinib at the time of the first formal interim analysis and patients who have disease progression according to central imaging review or ended treatment by the cutoff date for the second formal interim analysis for Cohort 1 after Amendment 3. The cutoff date for the second formal interim analysis is planned so that all the patients with FGFR2 gene fusions or translocations who received infiratinib at the time of the first formal interim analysis have 10 months follow-up after their initial exposure to infiratinib. The Sensitivity Analysis Set for Cohort 1 will be used for supportive sensitivity analyses for the second formal interim analysis for Cohort 1. Some analyses, including summary of demographic, baseline characteristics and disposition, and some key efficacy and safety analyses, will be repeated on the Sensitivity Analysis Set.

2.2.5 Interim Analysis Set for Cohort 3

The Interim Analysis Set for Cohort 3 will include the first 10 dosed subjects who have the potential to complete second scheduled post baseline scan.

2.2.6 *Per-Protocol Set*

The Per-Protocol Set (PPS) will consist of a subset of patients in the FAS who are compliant with requirements of the CSP in the following ways:

- Patient had an adequate tumor assessment at baseline
- Patient is evaluable for efficacy
- Patient had no CSR-reportable protocol deviations that may affect efficacy evaluation.

Subjects will be evaluable for efficacy if they have at least one post-baseline response assessed differently from 'unknown' or 'not assessed' as per RECIST v1.1. All CSR-reportable protocol deviations leading to exclusion from the PPS will be provided in a listing.

If more than 10% of FAS subjects were excluded from PPS, key efficacy analysis may be repeated on PPS.

2.2.7 *Pharmacokinetic analysis set*

The Pharmacokinetic analysis set (PAS) includes all patients who (a) receive the planned treatment, (b) provide at least one evaluable PK concentration, and (c) do not vomit within 4 hours after the dosing of infigratinib.

Subjects will be removed from the estimation of certain PK parameters on an individual basis depending on the number of available blood samples and whether the PK parameters can be reliably estimated based on the available blood samples. These patients will be identified at the time of the analyses.

2.2.8 *Subgroups of interest*

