2.3.1 Subject disposition

The following will be tabulated:

- Number (%) of patients treated;
- Number (%) of patients who are still on-treatment at the time of cut-off;
- Number (%) of patients who discontinued treatment and primary reasons for discontinuation.

A listing of disposition will be produced.

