ORR per investigator is among the secondary endpoints. The estimated ORR will be presented with the corresponding 95% confidence interval based on exact binomial distribution using the corresponding analysis set.

Overall Survival

Overall Survival (OS) is defined as the time from the date of start of treatment to the date of death due to any cause. The survival time for subjects without documentation of death prior to the data cutoff will be censored at the last date the subject was known to be alive prior to the cutoff date. Survival time for subjects with no post-baseline survival information will be censored at the date of start of treatment.

OS will be analyzed using the Kaplan-Meier method. Survival rate at 4, 6, 8, 12, 18, 24 months (and every 6 months thereafter as reported in database) with median OS will be estimated along with 95% confidence intervals.

Progression Free Survival

Progression free survival (PFS) is defined as the date of the start of treatment to the date of the event defined as the first documented progression or death due to any cause, whichever is earlier. If subject has not had an event, progression-free-survival is censored at date of last valid tumor assessment or start of study treatment if there is no valid tumor assessment available. For subjects who had an event after two or more missed visits, the subject will be censored at the last adequate tumor assessment. The PFS analyses will be done based on central and local assessments separately. Kaplan-Meier analysis of PFS will be provided.

The primary PFS will be derived based on all the tumor assessments and death including any after a subsequent anti-cancer therapy. A sensitivity analysis will also be conducted on PFS excluding the tumor assessments and death after any subsequent anti-cancer therapies. If the event (the first progressive disease or death) is after a subsequent anti-cancer therapy, the PFS for the sensitivity analysis will be censored at the last valid tumor assessment prior to all subsequent anti-tumor therapies or first dose date if there is no valid tumor assessment prior to all subsequent anti-tumor therapies.

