For Cohorts 2 and 3, the percentage of subjects who are progression-free at the second scheduled scan (approximately 16 weeks from treatment initiation) or later will be analyzed using 95% exact binomial confidence interval. Patients who do not have scans to show that they are progression-free at the second scheduled scan or later will be considered as not benefiting from the study treatment. Sensitivity analysis will be done by estimating PFS >16 weeks using K-M estimate.

Best Overall Response and Disease Control Rate

Overall lesion assessments will be listed by subject. BOR will be summarized for the rate of best overall response of progressive disease, stable disease, confirmed partial response (PR), and confirmed complete response (CR) separately; it will also be summarized for the Disease Control Rate which are the proportion of subjects having respectively a best overall response of confirmed PR or CR, or stable disease. The estimates will be presented along with the corresponding 95% exact confidence interval. Best overall response will be provided for investigator assessment and central assessment as specified by cohort (Section 1.2). In addition, the concordance of best overall response based on central assessment and local assessment will be assessed.

Best tumor burden change (maximum tumor burden reduction from baseline or minimum tumor burden increase from baseline if tumor burden has never reduced prior to any anti-cancer therapy) will be presented graphically.

Response Onset and Duration of Response

Response onset will be estimated using Kaplan-Meier product limit method to analyze TTR based on ORR central imaging assessment. The Brookmeyer-Crowley method will be used to construct the 95% CI for TTR. DOR will be further summarized by length of exposure to

infigratinib using the following exposure cut-off lengths: at least 6 months, at least 9 months, at least 12 months.

Response onset and duration of response (DOR) will be summarized for confirmed responders only, based on local and central assessments separately. Response onset is defined as the time from the first study drug administration date to the initial response date. DOR is defined as the time from the initial response to the date of the event defined as the first documented progression or death due to any cause, whichever is earlier. The same event/censoring rule applied to PFS will be applied to DOR.

2.7.2 *Safety Objectives*

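### The Sensitivity Analysis Set for the second Cohort 1 interim admits late-dosed patients only if they have progressed or stopped treatment, which skews disposition and would shorten central PFS and DOR

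*SAP*

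**What the plan says.** The main set for the second formal interim is Interim Analysis Set 2 (SAP 2.2.3), which "includes patients in Cohort 1 with FGFR2 gene fusions or translocations who have received at least one dose of infiratinib". It carries no outcome condition.

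The Sensitivity Analysis Set (SAP 2.2.4; same definition in Protocol 10.1.4) has two entry routes:

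- FGFR2-fusion or translocation patients who had received drug at the time of the first formal interim. The second cutoff is set so that they have 10 months of follow-up.
- "patients who have disease progression according to central imaging review or ended treatment by the cutoff date for the second formal interim analysis".

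The second route does not repeat the fusion restriction. I read it as fusion patients, because SAP 2.1 states: "The second formal interim analysis will be conducted on all the subjects with FGFR2 fusions or translocations in Cohort 1".

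On use of the set, SAP 2.2.4 says: "Some analyses, including summary of demographic, baseline characteristics and disposition, and some key efficacy and safety analyses, will be repeated on the Sensitivity Analysis Set". One row of the disposition table in SAP 2.3.1 is: "Number (%) of patients who are still on-treatment at the time of cut-off". The key efficacy analyses to be repeated are not named. SAP 2.6.1 attaches time to response and DOR to the primary ORR analysis.

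Patients without an event are already provided for in SAP 2.7.1: "If subject has not had an event, progression-free-survival is censored at date of last valid tumor assessment". For DOR: "The same event/censoring rule applied to PFS will be applied to DOR".

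**The concern.** For patients first dosed after the first interim, entry depends on the outcome being measured. A late patient who progressed or stopped is in; a late patient doing well on drug is out. Censoring already handles ongoing patients, so leaving them out adds nothing to a PFS or DOR estimate and removes follow-up that belongs in the risk sets.

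A sensitivity set of this kind should show whether short follow-up in late patients drives the Set 2 result. If PFS or DOR came out shorter here than in Set 2, the reader could not tell whether the data or the entry rule caused it. Disposition is named for repetition, so its still-on-treatment row is affected for certain. DOR is a likely repeat and PFS a possible one.

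**Working it through.** **1. Who is left out.** A late patient is excluded only if still on treatment and without central progression at the second cutoff. Death ends treatment (Protocol 4.1, Treatment period), so every excluded patient is alive. Each is therefore censored for central PFS and, if a responder, for central DOR.

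**2. Direction.** The Kaplan-Meier estimate is the product over event times of (1 - d/n), with d events and n at risk. Excluding a censored patient leaves every d unchanged and lowers n to n - 1 at event times up to that patient's censoring time. Since 1 - d/(n-1) ≤ 1 - d/n, each factor falls or stays equal, and so does the curve. This covers central PFS and DOR only. An excluded patient may have investigator-assessed progression, so local PFS is not covered, and neither is ORR.

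**3. The plan's precision figures (SAP 3.1).** The maximum exact (Clopper-Pearson) 95% half-width for ORR is 12.02 points at 36/72 (plan: 12%) and 9.87 points at 53/106 (plan: less than 10%). Both reproduce after rounding.

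**4. Number of late patients.** It is not stated. SAP 3.1 puts 72 fusion patients in Interim Efficacy Analysis Set 1 and at least 106 in the cohort. At 106, the late group is at most 106 - 72 = 34.

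**5. Size, by simulation.** These assumptions are not in the documents:

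- N = 106, with 34, 23 or 8 late patients.
- Late follow-up uniform from 0, 3 or 6 up to 10 months; early follow-up uniform 10-40 months.
- True ORR 25%; response onset at 2 months, confirmed if follow-up is at least 4 months.
- Time to central progression: responders 2.5 months plus an exponential with median 6; non-responders exponential with median 4.5. This gives a median PFS near 5.5 months. The documents' only figure is 175 days (175/30.4375 = 5.75 months), in the first 61 patients (Amendment 2 rationale).
- Treatment ends at progression.

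These 9 base cells were repeated with early follow-up 10-20 months, ORR 15% and 35%, and 15% and 30% other-reason stopping by 12 months: 9 × 6 = 54 cells of 2,500 replicates, 135,000 in all.

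Each entry below is Sensitivity set / Set 2 / set defined by dose date only. Medians are medians over replicates, in months.

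| Late patients, follow-up | Still on treatment, % | Median PFS | Median DOR | ORR, % | Dropped (confirmed responders) |
|---|---|---|---|---|---|
| 34, 0-10 mo | 5.2 / 22.6 / 6.3 | 4.62 / 5.48 / 5.38 | 5.50 / 6.47 / 6.29 | 23.1 / 21.8 / 25.0 | 19.4 (3.1) |
| 34, 6-10 mo | 5.0 / 15.8 / 6.5 | 4.67 / 5.40 / 5.36 | 5.06 / 6.50 / 6.29 | 23.5 / 25.2 / 25.2 | 12.1 (4.6) |
| 8, 0-10 mo | 6.1 / 10.2 / 6.3 | 5.25 / 5.44 / 5.36 | 6.14 / 6.37 / 6.30 | 24.6 / 24.2 / 25.0 | 4.6 (0.7) |

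First row: PFS shortfall 5.48 - 4.62 = 0.86 months; DOR shortfall 6.47 - 5.50 = 0.97 months. Over all 54 cells the shortfall is 0.12-0.97 months for PFS and 0.16-1.43 months for DOR. In none of the 135,000 replicates was median PFS, 6-month PFS or median DOR higher in the Sensitivity set than in Set 2. ORR shows no consistent direction.

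**6. Yardstick.** The simulated 95% sampling half-width of median PFS in Set 2 is 1.28-1.48 months. The documents' interval of 130 to 230 days in 61 patients gives (230 - 130)/2 = 50 days = 1.64 months.

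**7. A second model.** With progression detected on an 8-week scan grid and 34 late patients, mean median PFS was 5.68 against 6.46 months, DOR 6.04 against 6.93, and still on treatment 6.1% against 25.4%. With 5 late patients PFS was 6.36 against 6.44.

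**The case against.** **The set is supportive and the main harm is conditional.** PFS and DOR are not named for repetition, the primary endpoint is ORR, no decision rule uses the set, and the shift runs against the drug. All of this stands and limits the reach of the point.

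**Most of the on-treatment gap is follow-up maturity.** A dose-date set reads 6.3% against 5.2% with 34 late patients (0-10 months of follow-up), and 6.3% against 6.1% with 8. This also stands: the corrected row would look much the same. The difference is that its low value would come from at least 10 months of follow-up in everyone, not from removing ongoing patients.

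**Thirty-four late patients is an extreme.** It requires that no fusion patient outside Interim Efficacy Analysis Set 1 was dosed before the first cutoff. Protocol 10.7 treats that set and the Full Analysis Set as different at that interim, so the true number is probably lower and could be near zero. With no late patients there is no effect.

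**Continuous progression times overstate the shift.** The SAP censors at the last valid assessment and scans are every 8 weeks. With 34 late patients, last-scan censoring gave a mean paired PFS shortfall of 0.78 months against 0.82 with continuous times; a separate run gave 0.60-0.72 against 0.81-0.83. With 8 late patients the two runs gave 0.19 and 0.14-0.17 months. So the mean shift is little to moderately smaller with 34 late patients. The scan grid can hide it in the median of medians.

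**The rule has a purpose.** It adds late patients whose response is settled. That is arguable for ORR, but not for disposition, PFS or DOR.

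**Conclusion.** The concern holds. The direction is certain for central PFS and DOR: on this set they cannot exceed Set 2, and they fall whenever an excluded patient was at risk at an event time. The disposition summary loses late ongoing patients by rule, except any who continue drug after central progression.

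The size is uncertain because the number and follow-up of late patients are not given. Under the stated assumptions, with 8 to 34 late patients, the shortfall against Set 2 is about 0.1-1.0 months in median PFS and 0.2-1.4 months in median DOR. Even the largest PFS shift is below sampling error (1.3-1.6 months), but it always has the same sign. With 8 late patients it is negligible.

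Set 2 and the later primary Cohort 1 analysis are unaffected. This is a change worth considering, not a threat to the trial's main result.

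**What to change.** In SAP 2.2.4 and Protocol 10.1.4, delete the second entry route. Define the set as all Cohort 1 patients with FGFR2 gene fusions or translocations first dosed on or before the first formal interim cutoff, regardless of progression or treatment status at the second cutoff. These are the patients the plan already expects to have 10 months of follow-up. Name the repeated efficacy analyses (ORR, DOR and PFS), show them beside Set 2, and state how many Set 2 patients were first dosed later and their follow-up.

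If the sponsor wants to keep the present set to show settled responses, limit it to ORR and do not repeat disposition, PFS or DOR on it.

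The cost is one clause in two documents and a smaller set that loses late patients with settled responses. A protocol change needs an approved amendment (Protocol 12.1). If that is not wanted, the change can be made in the SAP and recorded in SAP Section 4, which now reads None. The maximum exact 95% half-width for ORR would be 12.0 points at n = 72 (the precision the plan accepts at the first interim), 11.2 at n = 83 (23 late) and 10.3 at n = 98 (8 late), against 9.9 at n = 106. The ORR-only alternative costs no precision.
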